#### **6.4. Patient Completion and Overall Study Completion**

Each patient will participate in the double-blind period for up to 28 days during screening, followed by 110 weeks of blinded treatment. At the end of the 110-week treatment period, treatment with study medication will be discontinued. Patients will return to the site for the end-of-blinded-treatment-period visit, 4 weeks after study medication has been discontinued. Thus, patients will participate in the study for a total of approximately 118 weeks.

A patient will be considered as having completed the double-blind period regardless of whether the patient is on or off study medication if the patient is followed until Week 114.

Patients who successfully complete the Week 114 visit will complete the assessments listed in the Schedule of Events ([Table 15.1-1](#) and [Table 15.1-2](#)). The visit data, including disposition of the patient, will be recorded on the appropriate eCRF.

Patients who complete the double-blind period may be eligible to enroll in the open-label extension period.

Eligible patients may participate in the open-label extension period for up to 156 weeks. If sparsentan becomes commercially available during the extension period, patients may transition out of the study onto commercial product before the end of the open-label extension period.

The study will be considered complete when the last patient completes his/her final visit.

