## 9. STUDY ASSESSMENTS

### 9.1. Schedules of Study Events

The Schedules of Study Events is located in [Section 15.1](#).

For all study sites in Germany, the measures related to the COVID-19 pandemic or other unexpected circumstances should be restricted to the COVID-19 pandemic. If an on-site visit by the patient is not feasible due to the challenges related to the COVID-19 pandemic, or other unexpected circumstances as dictated by local public health authority requirements, Investigators/appropriately designated study staff will be allowed to perform study visits as remote study visits (eg, conducted via telephone and video conference). These contacts will be allowed at all protocol-required visits and at any time during the conduct of the study. However, Screening, Day 1/Randomization, Week 110, and Week 114 visits must be conducted at the study site. The sites will discuss the patient's current health status, AEs, concomitant medications, and medication compliance during the telephone and video contacts. Patients will be instructed to contact the site personnel with any health concerns. Results of these patient contacts will be fully documented in the patient source documents/health records. Patients will return for an on-site visit as soon as the site and patient determine that it is appropriate and safe.

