#### **6.5.2. Study Day**

Study day 1 is defined as the day on which the first dose of study medication is administered (Day 1/Week 0). All other study days will be calculated relative to that date. The day before the start of study medication is Day -1 (there is no Day 0).

Study day will be calculated using the following formula:

- study day = date – first dose date + 1, where date  $\geq$  first dose date

- study day = date – first dose date, where date < first dose date

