### 6.5.4. Visit Windows

A visit window method will be applied to determine analysis visits across the study for efficacy and safety endpoints based on laboratory results, including eGFR and quantitative urinalysis (including UP/C). If a patient has multiple assessments (including unscheduled visits) within a visit window, the value closest to the target day for that visit will be selected for analysis. If more than 1 assessment is equidistant to the target day, then latest value will be selected. For efficacy analysis visits on or prior to Week 110, only assessments while the patient is on randomized treatment should be included (see [Section 8.1](#) for definition of on treatment).

The visit windows for the double-blind period shown in [Table 1](#) are defined for endpoints based on laboratory results. Visit windows for the OLE will be defined in a separate SAP.

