**Table 1: Visit Windows (Study Days)**

Analysis Visit	Relative Target Day	Analysis Visit Window (Study Days)	
		eGFR and Safety Labs	Quantitative Urinalysis
Week 2	15	2 – 22	N/A
Week 4	29	23 – 36	2 – 36
Week 6	43	37 – 64	37 – 64
Week 12	85	65 – 127	65 – 127
Week 24	169	128 – 211	128 – 211
Week 36	253	212 – 295	212 – 295
Week 48	337	296 – 372	296 – 372
Week 58	407	373 – 449	373 – 449
Week 70	491	450 – 533	450 – 533
Week 82	575	534 – 617	534 – 617
Week 94	659	618 – 701	618 – 701
Week 106	743	702 – 757	702 – 757
Week 110 	771	758 – 785	758 – 785
Week 114 	799	>785	>785
4-week After EOT 	799  or Last Dose Date + 28 	>785  or >Last Dose Date 	>785  or >Last Dose Date 

eGFR = estimated glomerular filtration rate; EOT = end of treatment.

 For patients who completed the planned randomized treatment period.

 Efficacy endpoints only.

 For patients who discontinued the randomized treatment early.

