## 8. EFFICACY

### 8.1. General Considerations

All efficacy analyses will be based on the FAS or PAS as described below. The primary and key secondary endpoint analyses will also be performed on the PP Analysis Set as supportive analyses. All primary efficacy analyses based on laboratory data will use central laboratory data only. All efficacy analyses specified below refer to the double-blind period only.

Proteinuria (UP/C) will be determined based on a 24-hour urine sample. As UP/C is a highly right-skewed variable, analyses will be performed on log-transformed data. For ease of interpretation, results will be presented in the original units.

The eGFR for each baseline and post-baseline visit will be determined using the Chronic Kidney Disease Epidemiology Collaboration ([Levey 2009](#)) formula for adults based on serum creatinine values from the visit.

For the purposes of efficacy analyses, an assessment is considered “on treatment” if it occurs after the first dose of study medication and no more than 3 days after the date of last dose of randomized treatment for the patient.

For all least squares (LS) means that include strata coefficients, the observed strata proportions will be used instead of assuming equal sizes of strata.

Longitudinal analyses of UP/C and eGFR (eg, via MMRM for continuous endpoints or generalized linear mixed models for binary endpoints) will consider data from post-baseline visits through Week 110 of the double-blind period. At the primary analysis, if there are issues with model converge due to sparsity of measurements at the later visits (ie, Week 106 or Week 110), then the longitudinal analyses will include only data through an earlier visit (ie, Week 94) to enable the analyses. The last visit to be included in the analyses will be appropriately documented in a note to file prior to unblinding for the primary analysis.

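### SAP Table 1 sets no off-drug condition on Week 114 for treatment completers, so an on-treatment value after Day 785 can be analysed as off-drug and drops out of the slope

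*SAP*

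**What the plan says.** SAP 6.5.4 assigns laboratory values, including unscheduled ones, to analysis visits by study day. If several fall in one window, "the value closest to the target day for that visit will be selected for analysis"; a tie goes to the latest. Treatment status enters once: "For efficacy analysis visits on or prior to Week 110, only assessments while the patient is on randomized treatment should be included". SAP 8.1 counts a value as on treatment if it is taken after the first dose and "no more than 3 days after the date of last dose of randomized treatment for the patient".

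Table 1 gives Week 110 as Days 758 to 785 (target 771) and Week 114 as any day after 785 (target 799). The only qualifier on these two rows is a footnote about the patient, not the assessment: "For patients who completed the planned randomized treatment period". The 4-week After EOT row reads ">785 1 or >Last Dose Date 3", where the trailing 1 and 3 are footnote markers for completers and early discontinuers. So early discontinuers get a window and a target (last dose + 28) tied to last dose, and completers get the calendar rule again.

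The protocol means the final visit to be off drug: "Patients will return to the site for the end-of-blinded-treatment-period visit, 4 weeks after study medication has been discontinued" (Section 6.4). Two exploratory eGFR endpoints use it: change from baseline to Week 114 (SAP 8.7.2) and change from Week 110 to Week 114 (SAP 8.7.3).

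**The concern.** The Week 114 endpoints are meant to show what remains once the reversible effect of the drug has gone. Under a pure calendar rule, a completer whose last on-treatment sample falls after Day 785 has that sample labelled Week 114. It can then displace the real off-drug value. The robustness analysis in SAP 8.7.2 does not help, because for completers the 4-week After EOT row applies the same cut at Day 785.

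The same sample also leaves the eGFR slopes. The chronic slope uses Week 6 to Week 110, and Week 110 is multiply imputed if nothing else falls in its window. For the total slope, SAP 8.1 stops longitudinal analyses at Week 110, while SAP 8.6.2 read alone would admit any on-treatment value. That conflict sits in the endpoint tested first in the US sequence.

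Late visits are foreseeable. SAP 7.3 plans for out-of-window visits, SAP 7.8 plans for pandemic disruption, and under Protocol 9.1 the "Screening, Day 1/Randomization, Week 110, and Week 114 visits must be conducted at the study site", so a late Week 110 visit cannot be replaced by a remote one.

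**Working it through.** **1. Inputs.** Study-day rule, SAP 6.5.2: "study day = date – first dose date + 1, where date" is on or after first dose. Windows and targets: SAP Table 1. Visit tolerances, Protocol Table 1: Week 110 ±14 days, Week 114 −7/+14 days.

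**2. Reproducing Table 1.** Target day = 7 × week + 1, so Week 110 = 771 and Week 114 = 799. Each upper bound is the midpoint to the next target: (743 + 771)/2 = 757 and (771 + 799)/2 = 785. The same two rules reproduce every other bounded upper limit in the table.

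**3. Who is affected.** In study days the protocol allows Week 110 on 771 ± 14 = 757 to 785, and Week 114 on 792 to 813. Late visits within tolerance (Days 772 to 785) therefore stay in Week 110. The first affected day is 786 = 771 + 15. (The earliest permitted day, 757, falls in the Week 106 window; that is a separate matter.)

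**4. Which value is selected.** Let D1 be the late on-treatment day (786 or later) and D2 the later off-drug day. D1 is nearer to 799 exactly when D1 + D2 > 2 × 799 = 1598; at equality the later value is taken.

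| Off-drug visit | Condition | Result |
|---|---|---|
| 28 days after D1 | 2 × 786 + 28 = 1600 > 1598 | late value selected for every D1 from 786 (Day 786: 13 days from target; Day 814: 15) |
| 21 days after D1 | 2 × D1 + 21 > 1598 | off-drug value selected for D1 = 786 to 788; late value from 789 |
| inside its own window, 792 to 813 | D2 > 1598 − D1 | D1 = 786 wins only against Day 813; D1 = 792 wins against Days 807 to 813 |
| missing | none | late value used |

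**5. A route with no visit deviation.** Protocol 7.2.2 lets the investigator repeat the Week 110 eGFR centrally before Week 114. Take Week 110 and last dose on Day 785. A repeat on Days 786 to 788 is within 3 days of last dose, so it is on treatment, yet it is labelled Week 114. Its distances from 799 are 13, 12 and 11 days; an off-drug visit on Day 785 + 28 = 813 is 14 days away. The repeat is selected. Here the Day 785 value still fills Week 110, so no imputation follows.

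**6. Effect on the slopes.** With every other visit present, the time spread of one patient in the chronic slope is Σw² − (Σw)²/n.

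- Eleven visits, Week 6 to Week 110: 51,516 − 646²/11 = 13,578 weeks², or 4.99 years².
- Without Week 110: 39,416 − 536²/10 = 10,686 weeks², or 3.93 years².
- Loss: about 21% for that patient. If 5% of patients were affected (an assumption; the documents give no figure), the loss over the trial is about 0.05 × 21% ≈ 1%.

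**7. Effect on the Week 114 mean.** If a share p of completers carries an on-drug value and the reversible effect is r, the arm mean moves by p × r. With p = 5% and r = 3 mL/min/1.73 m² (both assumed), that is 0.15; halving or doubling either input gives 0.075 or 0.30. In the change from Week 110 to Week 114, a patient with no other Week 110 value has nothing to subtract.

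**The case against.** The strongest reply is that the SAP and protocol windows meet exactly: the last permitted Week 110 day is the last day of the SAP window. No scheduled visit that keeps to the protocol is misclassified, and the documents give no count of visits 15 or more days late. This stands, and it limits the point to out-of-window visits and the narrow repeat-sample route.

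Second, a patient seen after Day 785 need not be on drug. Protocol 6.4 stops medication at the end of the 110-week period, and no study drug is dispensed at Week 110. Someone who stopped near Day 771 and is seen on Day 786 is more than 3 days past last dose, and is rightly kept out of Week 110. This also stands: the problem concerns only values that are on treatment by the SAP 8.1 definition. Such values are not far-fetched, because the schedule takes a pre-dose trough sample at Week 110, which presupposes dosing up to that visit.

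Third, if the final visit keeps its calendar window, the off-drug value often wins. That is true, and step 4 shows when. It does not return the late value to the slope.

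Fourth, both arms stop study drug and resume standard of care, so the treatment contrast moves only by the between-arm difference in the shift, not by the whole arm-level shift. This stands for the Week 114 endpoints.

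**Conclusion.** Wrong as written, with narrow scope and low impact. For completers, Table 1 can label an on-treatment value as the off-drug visit and remove it from the chronic slope, and from the total slope under SAP 8.1. This is a stated rule that gives the wrong answer, not an omitted detail. The sizes in steps 6 and 7 rest on an assumed frequency and an assumed reversible effect.

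Four stronger readings are tempting and not supported:

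- *That any late Week 110 visit is lost.* Visits up to Day 785 are handled correctly.
- *That the late value always displaces the off-drug one.* That is assured when the off-drug visit is 28 or more days later or missing; with a shorter gap it depends on the dates.
- *That the Week 110 tests would run on imputed values.* SAP 8.7.3 analyses those endpoints by MMRM without multiple imputation, so the value is simply missing there.
- *That confirmatory conclusions are at risk.* The Week 114 endpoints are exploratory and outside the testing sequence, and the expected loss in the slopes is small.

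A reader might also note that permitted windows allow 792 − 785 = 7 to 813 − 757 = 56 days off drug. That pairs opposite extremes of two protocol windows and takes last dose as the Week 110 visit date. It is not itself an error in Table 1.

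**What to change.** 1. In SAP Table 1, for completers, admit to Week 114 and to 4-week After EOT only values more than 3 days after last dose, with target last dose + 28, as already used for early discontinuers. A Day 786 on-drug value then no longer competes, and the Day 814 value becomes Week 114. Week 110 visits on Days 758 to 785 are unaffected.
2. Keep on-treatment values after Day 785 eligible for the Week 110 and slope analyses, and either use actual assessment time in the slope models or state an upper day limit. One of the two is needed because SAP 8.6.1 and 8.6.2 take time as the analysis visit in weeks: without a limit, a Day 820 value, at (820 − 1)/7 = 117 weeks, would enter as Week 110.
3. Align SAP 8.1 with SAP 8.6.2 on whether an on-treatment value after the Week 110 window belongs in the total slope.

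The cost is two lines in Table 1, a sentence in SAP 8.1 or 8.6.2, and the matching change to the derivation program, plus the time variable in the slope models if actual time is chosen. No new data are needed.

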**Table 1: Visit Windows (Study Days)**

Analysis Visit	Relative Target Day	Analysis Visit Window (Study Days)	
		eGFR and Safety Labs	Quantitative Urinalysis
Week 2	15	2 – 22	N/A
Week 4	29	23 – 36	2 – 36
Week 6	43	37 – 64	37 – 64
Week 12	85	65 – 127	65 – 127
Week 24	169	128 – 211	128 – 211
Week 36	253	212 – 295	212 – 295
Week 48	337	296 – 372	296 – 372
Week 58	407	373 – 449	373 – 449
Week 70	491	450 – 533	450 – 533
Week 82	575	534 – 617	534 – 617
Week 94	659	618 – 701	618 – 701
Week 106	743	702 – 757	702 – 757
Week 110 	771	758 – 785	758 – 785
Week 114 	799	>785	>785
4-week After EOT 	799  or Last Dose Date + 28 	>785  or >Last Dose Date 	>785  or >Last Dose Date 

eGFR = estimated glomerular filtration rate; EOT = end of treatment.

 For patients who completed the planned randomized treatment period.

 Efficacy endpoints only.

 For patients who discontinued the randomized treatment early.

### 6.5.5. Kidney Disease Quality of Life Survey

Kidney Disease Quality of Life (KDQOL)-36 is a short form questionnaire that includes the Short Form Health Survey (SF-12) as generic core plus the burden of kidney disease, symptoms/problems with kidney disease, and effects of kidney disease scales from the KDQOL-SF v1.3. Below are the included items:

- Items 1 to 12: SF-12 v2
- Items 13 to 16: Burden of kidney disease (4 items)
- Items 17 to 28: Symptoms/problems of kidney disease (12 items)
- Items 29 to 36: Effects of kidney disease (8 items)

Each question in KDQOL-36 is precoded with a numeric value, and out-of-range responses will be recorded as missing. Missing values will not be imputed. Survey responses will be scored based on adaptations from KDQOL-SF v1.3 scoring manual (Hays 1997) and SF-12 scoring guide (Maruish 2012), as outlined below:

1. For Items 13 to 36, raw pre-coded numeric values will be transformed to a possible range of 0 to 100, with the higher transformed scores always reflecting better QoL. Scores present the percentage of total possible scores achieved. Transformations per items are specified in Table 2 below.

**Table 2: Transformations of Pre-Coded Values for KDQOL-36**

Applicable Items	Pre-Coded Value	Transformed Score (0-100)
Items 13-16	1	0
	2	25
	3	50
	4	75
	5	100
Items 17-27, 28a, 28b, 29-36	1	100
	2	75
	3	50
	4	25
	5	0

KDQOL = Kidney Disease Quality of Life.

2. The 3 subscales shown in Table 3 will be computed as the average of available items (transformed scores) within each subscale:

**Table 3: KDQOL Subscales**

Subscale	Average of Available Items (Transformed Scores)
Symptoms/Problems List	Items 17-28 (12 items)
Effects of Kidney Disease	Items 29-36 (8 items)
Burden of Kidney Disease	Items 13-16 (4 items)

KDQOL = Kidney Disease Quality of Life.

3. For Items 1 to 12, scale scores and physical (PCS) and mental component summary (MCS) measures will be computed using a norm-based method in the steps shown in Table 4:

- Recode 4 items that require recoding, a higher score indicates better functioning:

**Table 4: SF-12 v2 Items Recoding**

Items	Response Choices	Pre-Coded Item Value	Final Item Value
1 – General Health	Excellent	1	5.0
	Very good	2	4.4
	Good	3	3.4
	Fair	4	2.0
	Poor	5	1.0
5 – How Much Did Pain Interfere with Your Normal Work	Not at all	1	5
	A little bit	2	4
	Moderately	3	3
	Quite a bit	4	2
	Extremely	5	1
6a – Felt Calm and Peaceful 6b – Energy	All of the time	1	5
	Most of the time	2	4
	Some of the time	3	3
	A little of the time	4	2
	None of the time	5	1

SF-12 = Short Form Health Survey.

- After item recoding, a raw score is computed for each scale. This score is the simple algebraic sum of responses for all items in that scale, as shown in Table 5 below:

**Table 5: SF-12 v2 Scale Items and Range of Possible Scores**

Scale	Sum of Final Item Values	Lowest and Highest Possible Raw Scores	Possible Raw Score Range
Physical Functioning (PF)	Items 2a + 2b	2, 6	4
Role Physical (RP)	Items 3a + 3b	2, 10	8
Bodily Pain (BP)	Item 5	1, 5	4
General Health (GH)	Item 1	1, 5	4
Vitality (VT)	Item 6b	1, 5	4
Social Functioning (SF)	Item 7	1, 5	4
Role Emotional (RE)	Items 4a + 4b	2, 10	8
Mental Health (MH)	Items 6a + 6c	2, 10	8

SF-12 = Short Form Health Survey.

- Transform each raw scale score to a 0 to 100 scale using the formula shown below:  

$$\text{Transformed scale} = \frac{(\text{Actual raw score} - \text{lowest possible raw score})}{\text{Possible raw score range}} \times 100$$
- Next, standardize each scale using a z-score transformation by subtracting the mean 0 to 100 score observed in the 1998 general United States (US) population for each scale and dividing the difference by the corresponding scale SD, as shown in Table 6 below:

**Table 6: SF-12 v2 Z-Score Transformation Based on 1998 General US Population Means and Standard Deviations**

Scale	Mean	Standard Deviation
Physical Functioning (PF)	81.18122	29.10558
Role Physical (RP)	80.52856	27.13526
Bodily Pain (BP)	81.74015	24.53019
General Health (GH)	72.19795	23.19041
Vitality (VT)	55.59090	24.84380
Social Functioning (SF)	83.73973	24.75775
Role Emotional (RE)	86.41051	22.35543
Mental Health (MH)	70.18217	20.50597

SF-12 = Short Form Health Survey; US = United States.

- Next, transform each scale z-score to the norm-based (50, 10) scoring. This is done by multiplying each z-score by 10 and adding the resulting product to 50. The norm-based scale scores will be used for analysis.

- To compute the PCS and MCS measures, multiply each scale z-score by its respective physical and mental factor score coefficient and sum the 8 products, as shown in Table 7 below:

**Table 7: SF-12 v2 Factor Score Coefficients for PCS and MCS Derivation**

Scale	Factor Score Coefficients	
	PCS	MCS
Physical Functioning (PF)	0.42402	-0.22999
Role Physical (RP)	0.35119	-0.12329
Bodily Pain (BP)	0.31754	-0.09731
General Health (GH)	0.24954	-0.01571
Vitality (VT)	0.02877	0.23534
Social Functioning (SF)	-0.00753	0.26876
Role Emotional (RE)	-0.19206	0.43407
Mental Health (MH)	-0.22069	0.48581

MCS = Mental component summary; PCS = Physical component summary; SF-12 = Short Form Health Survey.

- The final step for computation of PCS and MCS involves transforming the aggregate physical and mental summary scores to the norm-based (50, 10) scoring. This is done by multiplying each aggregate summary score from the previous step by 10 and adding the resulting product to 50. The norm-based scores will be used for analysis.

#### 6.5.6. EQ-5D-5L

EuroQol 5-dimension, 5-level quality of life (EQ-5D-5L) is a 2-part instrument consisting of the following:

- Descriptive system composed of the following 5 dimensions:
  - Mobility
  - Self-care
  - Usual activities
  - Pain/discomfort
  - Anxiety/depression
- EQ visual analogue scale (EQ VAS)

For each dimension, respondent will select 1 of 5 statements that best describe their health on that day. Each statement/level is pre-coded with a 1-digit number (1 to 5). Missing responses will be coded as “9”. The responses to the 5 dimensions are then concatenated to represent a patient’s health state. For example, “12345” represents mobility response of 1, self-care response of 2, usual activities response of 3, pain/discomfort response of 4, and anxiety/depression response of 5. The health states can be converted into a single index value based on country-specific value sets by using the crosswalk link function ([van Hout 2012](#)).

The EQ VAS records the respondent's self-rated health on a vertical, VAS. The scale is numbered from 0 to 100, with 0 labeled as "the worst health you can imagine" and 100 labeled as "the best health you can imagine."

## 6.6. Handling of Missing Data

Tabular summaries of missing data for efficacy endpoints will be prepared per [Section 7.8](#).

